Evaluation time for evaluation of treatment continuing group and treatment discontinued group in the third CRF should also be allocated separately for the data entered at the evaluation time of mTSS, bone erosion score and joint space narrowing score. For patients whom the final Humira treatment is later than week 52 +4 weeks, the data on the latest date in the third CRF should be used as the data on the final evaluation date of X-ray. However, if there is the date of survey discontinuation, the data up to the date should be used.

This date is called [final evaluation date of X-ray] in the following.

At final evaluation (third CRF)	
When the date of survey discontinuation is not entered: The final data of the patient among the data included in the period between the date of initial Humira treatment +504 days and the final evaluation date of X-ray (should be later than day 505) should be adopted.
 
When the date of survey discontinuation is entered: The final data of the patient among the data included in the period between the date of initial Humira treatment +504 days and the final evaluation date of X-ray (should be later than day 505) should be adopted.
 
In the treatment discontinued group, the data of which the date of treatment discontinuation and the final evaluation date of X-ray are ≥ 24 weeks apart should be adopted.

---------------------------------	--

When tabulating AEs by time of onset, the tabulation subjects should be decided based on the followings. If there is more than one event of the same PT in the same patient, its tabulation should be focusing on the initial occurrence.

However, when extraction conditions including seriousness and causal relationship are added to the AEs, its tabulation should be focusing on the initial occurrence after narrowing them down with the extraction conditions. In addition, the data on AEs outside the follow-up period among the data included in the following acceptable range should also be excluded from tabulation.

Timing and period category	Handling of data
Treatment start to week 24	Data included in the period between the date of initial Humira treatment and the date of initial Humira treatment +167 days should be adopted.
Week 24 to week 52	Data included in the period between the date of initial Humira treatment +168 days and the date of initial Humira treatment +363 days should be adopted.
Week 52 to week 108	Data included in the period between the date of initial Humira treatment +364 days and the date of initial Humira treatment +755 days should be adopted.
After completion of treatment	The data included in the AE follow-up period among the data on AEs occurred after completion of Humira treatment should be adopted.

13. Tables and figures to be prepared (numbers and names of Tables and Figures)

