7.2.1 Inclusion Criteria

The subjects of this study are patients with a diagnosis of RA and to whom adalimumab is prescribed as part of their normal treatment of RA. All subjects should be satisfying the following conditions.

- 1) Disease duration of RA ≤ 2 years
 - 2) MTX administration ≥ 3 months prior to starting adalimumab
 - 3) Dose of MTX ≥ 12 mg/week
-

4) DAS28-CRP >3.2

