4.2. Survey plan

(1) Survey subjects

Japanese RA patients who receive Humira meeting the following conditions.

- 1) Patients with the duration of RA within 2 years from the diagnosis at the start of Humira treatment
- 2) Patients receiving MTX for 3 months or longer at the start of Humira treatment
- 3) Patients receiving more than 12 mg/week of MTX at the start of Humira treatment
- 4) Patients with DAS28 (CRP) > 3.2 at the start of Humira treatment (4 weeks prior to treatment start - start date of treatment)

(2) Patients excluded from the survey

- 1) Patients who have received biological products

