RA stage/progression	Stage I, Stage II, Stage III, Stage IV, undescribed (It also should be tabulated by means of categories of “Stage I + II,” “Stage III + IV” and “undescribed” other than the above categories)
Disability level of RA	Class I, Class II, Class III, Class IV, undescribed (It also should be tabulated by means of categories of “Class I + II,” “Class III + IV” and “undescribed” other than the above categories)
Previous medication: DMARDs	Methotrexate (MTX), salazosulfapyridine, tacrolimus hydrate, bucillamine, others
Dose of concomitant MTX (mg/week) *1	$\geq 12.0\text{mg/week}$ and $< 14.0\text{mg/week}$, $\geq 14.0\text{mg/week}$ and $< 16.0\text{mg/week}$, $\geq 16.0\text{mg/week}$
Concomitant drug: DMARDs (other than MTX) *1	Present, absent
Concomitant drug: adrenocortical hormone *1	Present, absent

Data	Layer separation
Concomitant drug: DMARDs (other than MTX) *2	Present, absent
Concomitant drug: adrenocortical hormone *2	Present, absent
Concomitant drug: other concomitant drugs *2	Present, absent
DAS28-4CRP at Baseline by Category *3	<2.6, 2.6<=

*1 The concomitant drugs used at the start of Humira treatment should be included.

*2 The concomitant drugs used during the treatment with Humira should be included.

*3 The layer separation at the time of logistic regression analysis in the literature analysis should be applied.

<Treatment status>

Data	Layer separation
Mode of administration	Administration by a physician only, self-administration only, administration by a physician and self-administration
Period to treatment completion (day)*	≤ 168, ≥ 169 and ≤ 364, ≥ 365 and ≤ 728, continuing treatment *Continuing treatment should be ≥ 729 or the continued patients in the third CRF.
Dosage and administration	40 mg/biweekly, 80 mg/2 biweekly, 40 mg/biweekly or 80 mg/biweekly, other

* Patients confirmed to have longer treatment duration than 728 days and with “continuing” in the final record in the “treatment status” in the third CRF should be specified as the category of “continuing treatment.”

<Reason for discontinuation>

Data	Layer separation
Reason for discontinuation (first and second CRFs)	Occurrence of AEs, inadequate response, patient refused treatment with Humira, failed to visit hospital, others [symptoms improved (including complete remission), pregnancy/desire for pregnancy, others], undescribed

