Prior to treatment start	Data included in the period between the date of initial Humira treatment -28 days and the date of initial Humira treatment and the closest data to the date of initial Humira treatment should be adopted.
At week 12	Data included in the period between the date of initial Humira treatment +56 days and the date of initial Humira treatment +112 days and the closest data to the date of initial Humira treatment +84 days should be adopted.
At week 24	Data included in the period between the date of initial Humira treatment +140 days and the date of initial Humira treatment +196 days and the closest data to the date of initial Humira treatment +168 days should be adopted.
At week 52	Data included in the period between the date of initial Humira treatment +336 days and the date of initial Humira treatment +392 days and the closest data to the date of initial Humira treatment +364 days should be adopted.
At week 76	Data included in the period between the date of initial Humira treatment +504 days and the date of initial Humira treatment +560 days and the closest data to the date of initial Humira treatment +532 days should be adopted.
At week 104	Data included in the period between the date of initial Humira treatment +700 days and the date of initial Humira treatment +756 days and the closest data to the date of initial Humira treatment +728 days should be adopted.
At final evaluation	The final data of the patient among the data included in the period between the date of initial Humira treatment +1 day and the final evaluation date should be adopted.

For data entered at each evaluation timing of mTSS, bone erosion score and joint space narrowing score when evaluating efficacy regarding administration of Humira, the acceptability of data by timing should be judged based on the acceptable range of the timing. The acceptable range of the timing is shown in the table below.

If there is more than one data within the acceptable range of the timing, the data on the closest date to the reference date should be adopted. If there is more than one data within the acceptable range of the timing with the equal number of days from the reference before and after the reference date respectively, the data before the reference date should be adopted.

Additionally, it should follow the following provision for the data included in the following acceptable range.

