To handle the followings as the categorical data: [consultation category (outpatient, inpatient)], [gender (male, female)], [age category (< 15, ≥ 15 and < 30, ≥ 30 and < 50, ≥ 50 and < 65, and ≥ 65 and < 75, ≥ 75 and < 85, ≥ 85)], [age category: (< 15, ≥ 15 and < 65, ≥ 65)], [weight category (< 30, ≥ 30 and < 40, ≥ 40 and < 50, ≥ 50 and < 60, ≥ 60)], [category for duration of illness (< 3 months, ≥ 3 months and < 6 months, ≥ 6 months)], [complication (present, absent)], [smoking history (absent, present)], [RA stage/progression (Stage I/Stage II, Stage III/Stage IV)], [RA disability level (Class I/Class II, Class III/Class IV)], [past history (absent, present)], [history of allergy (absent, present)], [MTX at treatment start (≥ 12.0 mg/week and < 14.0mg/week, ≥ 14.0 mg/week and < 16.0mg/week, ≥ 16.0 mg/week)], [DMARDs at treatment start (excluding MTX) (absent, present)], [adrenocortical hormones at treatment start (absent, present)], [DMARDs during treatment (absent, present)], [adrenocortical hormones during treatment (absent, present)], [other concomitant drugs during treatment (absent, present)], [DAS28-4CRP at treatment start (< 2.6, 2.6 \leq)]; and also indicate the results for [age], [weight], [duration of illness] and [DAS28-4CRP at treatment start] as the quantitative data.

Note: This form should be prepared only at the time of literature analysis.

“Table 6.2.7.1 DAS28-4CRP Score of Week 24 and Mean Usage MTX dose Change from Week 24 to Week 52”

Analysis object: Patients included in the efficacy analysis set (DAS28-4CRP)

Purpose of analysis: Regarding the frequency of DAS28-4CRP Remission (< 2.6) at week 24, indicate from week 24 to week 52 by MTX dose reduction and compare them between the factors by χ^2 test.

Furthermore, a scatter graph with the DAS28-4CRP score at week 12 by patient as the Y axis and the change in MTX dose from week 24 to week 52 as the X axis should also be illustrated.

Note: The following tables should also be created with the same layout .

“Table 6.2.7.2 DAS28-4CRP Score of Week 24 and Mean Usage MTX dose Change from Week 24 to Week 104”

Note: The change in MTX dose from week 24 to week 104 should be compared in this form.

“Table 6.2.7.3 DAS28-4CRP Score of Week 12 and Mean Usage MTX dose Change from Week 12 to Week 52”

Note: The change in MTX dose from week 12 to week 52 and DAS28-4CRP Remission (< 2.6) at week 12 should be compared in this form.

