Purpose of analysis: To indicate the correlation with the patient background items for the patients who achieved mTSS change below 0.5 at week 52. Patient background items and categories are shown below.

<Patient background item>	<Included data>
Consultation category	Outpatient, inpatient
Gender	Male, female
Age	Continuous value
Age category 1	Aged < 15, 15<= <30, 30<= <50, 50<= <65, 65 <= < 75, 75<= < 85, <= 85
Age category 2	Aged < 15, 15 <= <65, <=65
Weight	Continuous value
Weight category	< 30, 30<= <40, 40<= <50, 50<= <60, <=60
Duration of illness	Continuous value
Category of duration of illness	< 3, 3<= <6, <=6
Complication	Present, absent
Smoking history	Present, absent
RA stage/progression	Stage I, Stage II, Stage III, Stage IV
Disability level of RA	Class I, Class II, Class III, Class IV
Past history	Present, absent
History of allergy	Present, absent
MTX at treatment start	<=12.0 <14.0, <=14.0 <16.0, <=16.0
DMARDs at treatment start (excluding MTX)	Present, absent
Adrenocortical hormones at treatment start	Present, absent
DMARDs during treatment	Present, absent
Adrenocortical hormones during treatment	Present, absent
Other concomitant drugs during treatment	Present, absent

DAS-28CRP at treatment start	Continuous value
Category of DAS-28CRP at treatment start	<2.6,2.6<=

Note: To indicate Spearman rank correlation coefficient and its p value should be indicated for correlation coefficient.

This form should be prepared only at the time of literature analysis.

“Table 6.9.4.2 Correlation of Subjective background (Spearman's rank correlation coefficient) at the mTSS Remission by Week 104”

Analysis object: Patients included in the efficacy analysis set (mTSS at week 104)

Purpose of analysis: To indicate the correlation with the patient background items for the patients who achieved mTSS change below 0.5 at week 104 by using the same technique as Table 6.9.4.1.

“Table 6.9.5.1 Univariate logistic analysis event: ≤ 0.5 delta mTSS at 52 week”

Analysis object: Patients included in the efficacy analysis set (mTSS at week 52)

Purpose of analysis: To conduct univariate logistic regression analysis with the number of patients meeting the week-52 mTSS change ≤ 0.5 as the objective variable and each patient background factor as the explanatory variable, and to indicate the number of patients analyzed, number of patients who developed ADRs, incidence rate, odds ratio, CI and p values.

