To handle the followings as the category data: [consultation category (outpatient, inpatient)], [gender (male, female)], [age category (< 15 , ≥ 15 and < 30 , ≥ 30 and < 50 , ≥ 50 and < 65 , and ≥ 65 and < 75 , ≥ 75 and < 85 , ≥ 85)], [age category: (< 15 , ≥ 15 and < 65 , ≥ 65)], [weight category (< 30 , ≥ 30 and < 40 , ≥ 40 and < 50 , ≥ 50 and < 60 , ≥ 60)], [category for duration of illness (< 3 months, ≥ 3 months and < 6 months, ≥ 6 months)], [complication (present, absent)], [smoking history (absent, present)], [RA stage/progression (Stage I/Stage II, Stage III/Stage IV)], [RA disability level (Class I/Class II, Class III/Class IV)], [past history (absent, present)], [history of allergy (absent, present)], [MTX at treatment start (≥ 12.0 mg/week and < 14.0 mg/week, ≥ 14.0 mg/week and < 16.0 mg/week, ≥ 16.0 mg/week)], [DMARDs at treatment start (excluding MTX) (absent, present)], [adrenocortical hormones at treatment start (absent, present)], [DMARDs during treatment (absent, present)], [adrenocortical hormones during treatment (absent, present)], [other concomitant drugs during treatment (absent, present)], [DAS28-4CRP at treatment start (< 2.6 , $2.6 \leq$)]; and also indicate the results for [age], [weight], [duration of illness] and [DAS28-4CRP at treatment start] as the quantitative data.

Note: This form should be prepared only at the time of literature analysis.

“Table 6.9.5.2 Univariate logistic analysis event: ≤ 0.5 delta mTSS at 104 week”

Analysis object: Patients included in the efficacy analysis set (mTSS at week 104)

Purpose of analysis: To tabulate the number of patients satisfying week 104 mTSS change below 0.5 as the objective variance by using the same technique as Table 6.9.5.1.

“Table 6.9.6.1 Multivariate logistic analysis event: ≤ 0.5 delta mTSS at 52 week”

Analysis object: Patients included in the efficacy analysis set (mTSS at week 52)

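### The SAP splits baseline DAS28-4CRP at 2.6 although entry requires a score above 3.2, so one level is empty or nearly empty by design in five exploratory tables

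*SAP*

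**What the plan says.** **Entry.** Protocol 7.2.1 requires "DAS28-CRP >3.2" and gives no measurement window. SAP 4.2 repeats the threshold and adds the window: "Patients with DAS28 (CRP) > 3.2 at the start of Humira treatment (4 weeks prior to treatment start - start date of treatment").

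**Analysed baseline.** SAP section 12 takes the pre-treatment value from "Data included in the period between the date of initial Humira treatment -28 days and the date of initial Humira treatment", using the value closest to the first dose.

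**The factor.** SAP section 11 lists "DAS28-4CRP at Baseline by Category" with two levels, below 2.6 and 2.6 or above. Its footnote *3 says when the split applies: "The layer separation at the time of logistic regression analysis in the literature analysis should be applied".

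**Where it is used.**
- Table 6.2.6 (univariate logistic, week-104 remission) lists "DAS28-4CRP at treatment start (< 2.6, 2.6" or above) among the categorical factors. Table 6.9.5.1 (univariate logistic, week-52 mTSS change) has the same entry, and Table 6.9.5.2 follows it for week 104.
- Table 6.9.4.1 (Spearman, week-52 mTSS) lists "Category of DAS-28CRP at treatment start" with the same cut, and Table 6.9.4.2 follows it for week 104.

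All five tables also use baseline DAS28-4CRP as a continuous variable.

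**The concern.** A cut at 2.6 separates patients in remission from the rest. That is a sensible outcome category, but this study admits only patients with moderate or high activity, so as a baseline factor it has nobody to put in the lower level. A two-level factor that loses one level is a constant and cannot explain anything.

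If the lower level is truly empty, the row yields no result. If a few patients with a baseline below 2.6 stay in the analysis set, the row may print an odds ratio or a coefficient. That number would compare a handful of eligibility exceptions with everyone else, yet it would be labelled as an effect of baseline disease activity. The second outcome is the worse one, because the number could be quoted.

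**Working it through.** The plan gives no figure for this split, so there is none to reproduce. The check compares the definitions and then asks what happens if a few exceptions remain.

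**1. Same measure.** Protocol 7.6.3 builds DAS28 from tender joints, swollen joints, ESR or CRP, and the patient's assessment. SAP 10.3 builds DAS28-4CRP from the same four components with CRP. The entry score and the analysed score appear to be the same quantity.

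**2. Same window.** SAP 4.2 uses the 4 weeks up to treatment start. SAP section 12 uses day −28 to first dose, and 4 × 7 = 28 days.

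**3. Levels.** No value is both above 3.2 and below 2.6. Every patient who meets the criterion on the analysed value is in the upper level, whatever the sample size.

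**4. Lower level empty.** The logistic design matrix (intercept plus indicator) has two identical columns and rank 1, so no odds ratio can be estimated. Spearman's coefficient divides by the standard deviation of the ranks, which is zero, so the coefficient and its p value are undefined. A numerical check with 171 records gave rank 1 and no Spearman value. With a continuous covariate the rank was 2 and the coefficient computable.

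**5. Lower level holds k exceptions.** The number k is an assumption; the documents give none. For illustration, take N = 171, the plan's evaluable number for week 52, and the same event rate p = 0.55, the plan's expected week-52 remission rate, in both levels. The 171 does follow from the plan's inputs: [1.960·√(0.427·0.573) + 1.282·√(0.55·0.45)]² / 0.123² = 170.7. Neither N nor p is given for week 104 or for mTSS.

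- Probability that the lower level is all events or all non-events, so that no finite odds ratio exists: p^k + (1−p)^k.
- Standard error of the log odds ratio at expected counts: √[1/(kp) + 1/(k(1−p)) + 1/((N−k)p) + 1/((N−k)(1−p))].
- Ratio of upper to lower 95% limit: exp(2 × 1.96 × SE).

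| k | P(no finite odds ratio) | SE | Upper/lower 95% limit |
|---|---|---|---|
| 0 | no contrast | – | – |
| 1 | 1.00 | – | – |
| 2 | 0.51 | 1.43 | 272 |
| 3 | 0.26 | 1.17 | 98 |
| 5 | 0.07 | 0.91 | 36 |
| 10 | 0.003 | 0.66 | 13 |

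For k = 5: SE = √(0.364 + 0.444 + 0.011 + 0.013) = 0.91, and exp(3.92 × 0.912) ≈ 36.

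**6. Sensitivity to N and p.** The lower level alone contributes 1/(kp) + 1/(k(1−p)) to the variance. This is smallest at p = 0.5, where it equals 4/k. With k = 5 and an unlimited number of patients in the upper level, SE is at least √0.8 = 0.894 and the limit ratio at least exp(3.92 × 0.894) ≈ 33. At N = 350 and p = 0.55 it is 35. The imprecision comes from k, so recruiting more eligible patients does not cure it.

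**7. Alternative split.** SAP section 11 already classes DAS28-4CRP as moderate (above 3.2, up to 5.1) and high (above 5.1). Eligible patients can occupy both. The documents give no baseline distribution, so the two counts cannot be computed.

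**The case against.** Four points can be made for the plan as it stands.

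**The level may not be exactly empty.** The split applies to the efficacy analysis set. SAP section 8 places that set's exclusion rules in a separate handling-criteria document that is not among those reviewed, so patients who fail the DAS28 criterion might be retained. A patient with two values in the 28-day window could also qualify on one and be analysed on the other. This stands. A reader might infer that the row is certain to return nothing in all five tables; the documents do not support that. It does not rescue the split, because steps 5 and 6 of the working show that a few exceptions give no usable contrast.

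**The predictor is not lost.** A reader might infer that the SAP fails to examine baseline disease activity. It does examine it, as a continuous variable in the same tables. This stands in full and limits the point to the categorical row.

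**Incalculable results are handled.** SAP 9.5 prints a hyphen when a figure cannot be calculated. That covers an empty level. It does not cover one with several exceptions, where a number would be printed.

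**The tables are peripheral.** Footnote *3 ties the split to the literature analysis, and the notes to Tables 6.2.6, 6.9.4.1 and 6.9.5.1 restrict them to it. The analyses are exploratory. This also stands.

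**Conclusion.** The split is wrong as written, and the effect is small. For patients who meet the entry criterion on the analysed value, the factor is constant. In practice its lower level is empty or holds at most a few exceptions, so the odds ratio or correlation is inestimable or uninformative at any sample size. This affects one categorical row in each of five exploratory tables.

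The continuous baseline DAS28-4CRP results are unaffected. So are the primary week-52 remission endpoint, the sample size and the multivariate mTSS models in Tables 6.9.6.1 and 6.9.6.2, which do not include baseline DAS28.

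The conclusion assumes that entry and analysis use the same CRP-based score, as the component lists indicate, and that few patients below 2.6 are retained. The matching window comes from SAP 4.2 and section 12; Protocol 7.2.1 sets none. It would be tempting to attach a denominator, such as half of 350, but that rests on the week-52 dropout assumption. The documents give no such rate for week 104 and no size for the mTSS subsets. The point is logical and needs no denominator.

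**What to change.** In the SAP section 11 row marked *3, and in Tables 6.2.6, 6.9.4.1, 6.9.4.2, 6.9.5.1 and 6.9.5.2, replace the 2.6 split with the SAP's own DAS28-4CRP classes: moderate (above 3.2 and up to 5.1) versus high (above 5.1). The change belongs in the table row, because footnote *3 only says when the split applies. State that any retained patient with a baseline of 3.2 or below is listed separately and left out of this contrast.

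Deleting the categorical row and relying on the continuous result is an equally sound alternative. It may be the better one if the high class proves small, since the balance between moderate and high is unknown.

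Either change costs SAP wording and matching table programming. No new data are needed.

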7.0 Study Objective (s)

In daily clinical setting, patients with RA who receive adalimumab (Humira[®]) and high-dose MTX (≥ 12 mg/week) will be observed prospectively and the effectiveness will be assessed by DAS28 and mTSS. In addition the safety of the combination of adalimumab and high dose MTX will be assessed in terms of the incidence and pattern of the occurrence of adverse events.

The primary objective of the study is to assess the clinical effectiveness of adalimumab in combination with high dose MTX (≥ 12 mg/week). This will be measured by assessing the percentage of patients with the DAS28 score of < 2.6 at week 52.

The secondary objective of the study is to assess the clinical effectiveness of adalimumab in combination with high dose MTX (≥ 12 mg/week) by assessing the proportion of patients with a change in the following variables from baseline to week 104:

- Clinical Disease Activity Index (CDAI)
-

- Simplified Disease Activity Index (SDAI)
- The severity of functional impairment (HAQ)
- The health-related quality of life (EQ-5D)
- The inhibition of structural progression will be assessed by measuring the modified Van der Heijde Total Sharp Score (mTSS).

The safety profile will be assessed by measuring the following variables:

- All serious adverse events (SAEs) and adverse events (AEs)

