7.5 Study Duration

- 1) The duration of the whole PMOS is estimated to be about 4 years.

- Study start: September 2012
-

- Recruiting phase: September 2012 - December 2014
 - Data completion: January 2018
 - End of study: The date on which statistical analysis dataset for Clinical Study Report becomes available
 - Data analysis and final report: April 2018 – October 2018
- 2) For each individual patient, the PMOS starts with the enrollment at the beginning of the treatment with adalimumab.
- Observation period
 - 104 weeks (or discontinuation of this study)
 - Discontinuation of this study
 - Patients within 52 weeks into this study: When adalimumab treatment is discontinued.
 - Patients after 52 weeks into this study: When any biologics other than adalimumab is administered.

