13.3 Missing Values

Missing observations will be documented as missing values. Instructions for the minimum documentation required for a patient to be evaluable will be established in the

SAP.

All data will be analyzed on the basis of “observed cases”. For the statistical analysis of data concerning the course of disease (if related to changes from baseline values), an additional approach will be followed considering only patients with complete data at all visits.

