Reason for discontinuation (third CRF)	Occurrence of AEs, symptom improved, inadequate response, patient refused treatment with Humira, others (pregnancy/desire for pregnancy, others), undescribed
Reason for survey discontinuation	Administration of biological products other than Humira, failed to visit hospital, others, undescribed

<Efficacy endpoints>

Data	Layer separation	
DAS28-4ESR	High Moderate Low Remission	> 5.1 > 3.2 and ≤ 5.1 ≥ 2.6 and ≤ 3.2 < 2.6
DAS28-4CRP	High Moderate Low Remission	> 5.1 > 3.2 and ≤ 5.1 ≥ 2.6 and ≤ 3.2 < 2.6
CDAI	High Moderate Low Remission	> 22.0 > 10.0 and ≤ 22.0 > 2.8 and ≤ 10.0 ≤ 2.8
SDAI	High Moderate Low Remission	> 26.0 > 11.0 and ≤ 26.0 > 3.3 and ≤ 11.0 ≤ 3.3
HAQ-DI	High Moderate Low Remission	> 1.5 > 1.0 and ≤ 1.5 > 0.5 and ≤ 1.0 ≥ 0 and ≤ 0.5
mTSS	Change (≤ 0) Change (≤ 0.5) Change (≤ 1.0)	Change ≤ 0 Change ≤ 0.5 Change ≤ 1.0
Bone erosion score	Change (≤ 0) Change (≤ 0.5) Change (≤ 1.0)	Change ≤ 0 Change ≤ 0.5 Change ≤ 1.0
Joint space narrowing score	Change (≤ 0) Change (≤ 0.5) Change (≤ 1.0)	Change ≤ 0 Change ≤ 0.5 Change ≤ 1.0

*Hereafter, “complete remission” refers to “Remission” in the above table.

12. Handling of data on test/evaluation time

For data entered at each timing of efficacy evaluation excluding mTSS, bone erosion score and joint space narrowing score, the acceptability of data by timing should be judged based on the acceptable range of the timing. The acceptable range of the timing is shown in the table below.

If there is more than one data within the acceptable range of the timing, the data on the closest date to the reference date should be adopted. If there is more than one data within the acceptable range of the timing with the equal number of days from the reference before and after the reference date respectively, the data before the reference date should be adopted.

When evaluating efficacy regarding administration of Humira, it should follow the following provision for the data included in the following acceptable range.

- The data up to the date of final Humira treatment + 28 days should be tabulated.

However, the date of final Humira treatment +28 days is later than the date of survey discontinuation, the data up to the date of survey discontinuation should be tabulated.

This date is called [final evaluation date] in the following.

Timing and period category	Handling of data

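### The week-76 and week-104 clinical efficacy rows are on-drug results without being labelled so, and no table gives a week-104 result for all patients still observed

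*SAP*

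**What the plan says.** **Protocol.** Section 7.5 has two rules for the end of observation. Up to week 52, stopping adalimumab ends it. After that, the trigger is different: "Patients after 52 weeks into this study: When any biologics other than adalimumab is administered". Section 7.0 sets the secondary objective as the "proportion of patients with a change in the following variables from baseline to week 104", naming CDAI, SDAI, HAQ, EQ-5D and mTSS. Section 13.3 bases all analyses on observed cases, with no condition on current adalimumab use. For course-of-disease data expressed as change from baseline it adds that "an additional approach will be followed considering only patients with complete data at all visits".

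**SAP.** Section 12 introduces its cut-off with "When evaluating efficacy regarding administration of Humira, it should follow the following provision for the data included in the following acceptable range", and then states: "The data up to the date of final Humira treatment + 28 days should be tabulated". If survey discontinuation comes earlier, that date applies instead. The week-76 window lies between "the date of initial Humira treatment +504 days and the date of initial Humira treatment +560 days", and the week-104 window between "the date of initial Humira treatment +700 days and the date of initial Humira treatment +756 days". Tables 6.1 to 6.6 report by these evaluation times.

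Sections 8, 10.1 and 12 also define a third-CRF efficacy set, a treatment-continuing group, a treatment-discontinued group and a separate final evaluation that may fall well after the last dose. Table 6.1.2 reports the clinical endpoints for these two groups. Table 6.9.2 does the same for mTSS, and List 8.2 lists third-CRF patients.

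**The concern.** Up to week 52 the cut-off has little to act on, because observation ends when adalimumab does. After week 52 the protocol deliberately keeps watching patients who stop, and the SAP keeps most of what it sees out of the by-visit rows.

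Stopping is unlikely to be unrelated to outcome. The SAP's own third-CRF reasons for discontinuation (section 11) include both improved symptoms and inadequate response. A trend from week 52 to week 104 in Tables 6.1 to 6.6 therefore mixes how patients fared with who remained on drug. A reader of the secondary week-104 results would not learn this from the table titles or notes.

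**Working it through.** **1. The plan's own figure.** No figure in the plan concerns weeks 76 or 104. The sample size rests on week 52 only, and it reproduces. For a one-sample test of 55% against 42.7%, two-sided 5% and 90% power:

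n = [(1.960·√(0.427·0.573) + 1.282·√(0.55·0.45)) / 0.123]² = 170.7, so 171; and 171/0.5 = 342, set at 350.

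Nothing below changes it.

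**2. Who can enter the by-visit rows.** Days are counted from first Humira treatment. A value counts only if it lies in the window and no later than the last Humira date + 28.

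- Week 76: earliest qualifying last date = 504 − 28 = day 476.
- Week 104: earliest qualifying last date = 700 − 28 = day 672.

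These are minimum conditions. A patient seen exactly on day 728 needs a last date of 728 − 28 = day 700 or later. In the other direction, SAP 10.1 takes the latest completion date as the last Humira date, so a patient who paused and restarted still counts. Hence the rows are essentially, not strictly, on-drug.

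**3. Who can enter the discontinued group of Table 6.1.2**, among patients followed to week 104:

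- The third-CRF set needs a last date after week 52 + 4 weeks: 364 + 28 = 392, so from about day 393. It also needs DAS28-4CRP at baseline, in the week-52 window, and from the lower limit of the week-76 window onward.
- The discontinued group needs at least 24 weeks between stopping and week 104: 728 − 168 = day 560 at the latest.

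**4. The two rules side by side**, for last Humira dates after week 52 and before day 672:

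| Last Humira date | Days | Week-104 row | Table 6.1.2 discontinued group |
|---|---|---|---|
| 365–392 | 28 | no | no |
| 393–560 | 168 | no | yes, if the required values exist |
| 561–671 | 111 | no | no |

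The total is 28 + 168 + 111 = 307 days, of which 28 + 111 = 139 lead to neither summary. If stops were spread evenly over this span (an assumption), 139/307 = 45% of these patients would be in neither.

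**5. What Table 6.1.2 offers instead.** The only timing rule given for its off-drug values is the last value from day 504 onward, not week 104. It has no row pooling the two groups. Its category output is described as patient counts, without the percentages, 95% intervals and McNemar tests specified for Tables 6.1 to 6.4.

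**6. Effect on a remission rate.** Let s be the share of patients observed at week 104 who are left out of the row, r₁ the remission rate in the row, and r₀ the rate in those left out. Then

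row − all observed = r₁ − [(1 − s)·r₁ + s·r₀] = s·(r₁ − r₀).

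The documents give none of the three. Assumed ranges: s 10–40%, r₁ 55–70%, r₀ 20–60%.

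- Lowest: 0.40·(0.55 − 0.60) = −0.02.
- Highest: 0.40·(0.70 − 0.20) = +0.20.
- Example: s = 20%, 70% against 40%: all observed = 0.8·0.70 + 0.2·0.40 = 64%, against 70% in the row.

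**7. Complete-data analysis.** No table in SAP section 13 restricts to patients with data at every visit. The third-CRF set requires three time points, which is a weaker condition.

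**The case against.** The strongest reply is that this is a coherent design. The objective concerns adalimumab combined with high-dose MTX, and the cut-off is expressly confined to evaluating efficacy under Humira administration. On that view an on-drug row by visit, with a separate table for patients who stopped, answers the question asked. That stands as a defence of keeping the on-drug row. It does not explain why the row is unlabelled, or why Protocol 13.3 states no such limit.

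A reader might infer that the plan throws the off-drug data away. It does not. Tables 6.1.2 and 6.9.2 use them, and List 8.2 covers third-CRF patients. The third-CRF version of Table 1.2 counts all four groups, including those not summarised in Table 6.1.2. Tables 6.1 to 6.6 also have a final-evaluation time point that keeps each stopper's last on-drug value.

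A reader might also infer that all secondary week-104 results are affected. mTSS has its own +56-day rule, unclearly worded, and its own tables, so it is outside this point.

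Nor is the direction of any distortion wholly hidden. Table 3.2.2 gives reasons for stopping, Tables 5.8.1 and 5.8.2 show continuation to week 104, and Table 6.1.2 shows scores for some stoppers. These are clues to direction; they do not supply the missing week-104 estimate.

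Finally, visit rows hold different patients under any observed-case analysis. That is true and would remain so in the added row. The narrower complaint is the extra selection by drug status.

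**Conclusion.** The point holds in a limited form. The clinical week-76 and week-104 rows of Tables 6.1 to 6.6 are essentially on-drug results. No table gives a pooled week-104 clinical result for all patients still under observation. Stops on about days 365–392 and 561–671 reach neither the week-104 row nor the discontinued group. The day limits follow from the SAP's windows; the 45% share rests on evenly spread stopping.

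It would be tempting to conclude that the planned week-104 rates are too high. The documents do not support a sign or a size: the −2 to +20 point range comes entirely from assumed inputs and crosses zero. The week-52 primary endpoint and the sample size are unaffected. The missing complete-data analysis is a separate, plain gap between Protocol 13.3 and the SAP, and is best closed in the same edit. Overall this is an inexpensive improvement, not a flaw that undermines the study.

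**What to change.** - Label the existing week-76 and week-104 rows of Tables 6.1 to 6.6 as on-drug (values up to 28 days after the last Humira date), and state in SAP section 12 that this is the intended estimate.
- Beside each, add an observed-case row using every value in the window up to the date of survey discontinuation, regardless of adalimumab use. Leave missing values missing, in line with SAP 9.1, and report how many patients left because another biologic was started. Counting those patients as not in remission would be imputation, which SAP 9.1 rules out, so it is not part of this change.
- Add the version of the change-from-baseline tables restricted to patients with complete data at all visits, as Protocol 13.3 promises, and say whether on-drug or all observed values define completeness.

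The protocol already schedules the data. The cost is SAP wording and extra rows, and the report will have two week-104 figures to explain.
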